In subjects with stable coronary heart disease (CHD) and inducible ischemia, percutaneous coronary interventions (PCI) can improve symptoms. As coronary angiography is often inexact in accurately determining the functional significance of non-critical coronary stenoses, fractional flow reserve (FFR) can assess their physiological significance¹². For subjects with acute coronary syndromes and multivessel disease undergoing an early invasive strategy, performing PCI in the culprit vessel and 'staging' possible treatment allows measurement of non culprit FFR at initial angiography. While non-culprit FFR in Acute Coronary Syndrome (ACS) subjects may worsen acutely due to endothelial dysfunction, randomisation should minimise confounding. Return for planned staged PCI as guided by angiography has been standard practice in such subjects, and increasingly, revascularisation is FFR guided. We plan to perform another FFR study to evaluate flow changes over a three month period.

The coronary circulation is comprised of two major components: the major epicardial coronary arteries which have a capacitance function; and the microvascular circulation comprised of pre-arterioles and arterioles which provide a metabolic interface with cardiac myocytes.¹³ Both components of the circulation have been implicated in coronary ischaemia. By measuring pressure and flow in the epicardial coronary artery, indices to assess the microcirculation can be calculated such as CFR, IMR, HSR, HMR at the same time as calculating the FFR value. This provides a comprehensive physiological assessment of the entire coronary circulation¹⁴. We plan to record pressure and flow indices at the time of measurement of FFR in the culprit and non-culprit arteries.

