3. STUDY DESIGN

This is a Phase II a, prospective study comprising of 60 subjects referred to Liverpool Hospital and Sydney Southwest Private Hospital who have paired FFR assessments. To achieve this number, assuming a dropout rate of 25%, approximately 80 subjects will be approached. These subjects will be undergoing investigation for **symptomatic CHD**. Once consent has been obtained and the subject has met all the inclusion criteria without exclusions, they will be included in the study. The study is a randomised, placebo controlled trial at a randomisation rate of 1:1.

The primary endpoint will be a 20% reduction in the rate of FFR <0.80 in subjects planned to undergo staged PCI at 3 months among those randomly assigned to ACAC therapy. That is a difference of 6 or more in the ACAC group who had an FFR <0.80 at onset will have a FFR ≥0.80 at 3 months than in control group.

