4. SELECTION OF STUDY POPULATION

4.1 Inclusion Criteria

The subject must meet all of the following criteria to be eligible for inclusion in the study:

1. Males and females (without childbearing potential as evidenced by hysterectomy, tubal ligation or at least one year post-menopause) aged 18 to 80 years, inclusive.
2. Ability to provide written informed consent to participate in the study.
3. Subjects with documented recent acute coronary syndrome (ACS) or evidence of myocardial ischemia.
4. Subjects who have a culprit lesion suitable for PCI, and a non-critical lesion in another vessel suitable for staged PCI with an FFR of ≤ 0.80 , for subjects undergoing diagnostic angiography and FFR without ad hoc PCI. Or subjects who have a single non-critical culprit lesion of intermediate severity with a clinically indicated FFR ≤ 0.80 which is suitable for staged PCI.
5. No serious co-morbidities, which might interfere with the subject's ability to enter the study.
6. Able to communicate effectively with the study team and to comply with the protocol.

4.2 **Exclusion Criteria**

The subject must be excluded for any of the following reasons:

1. Females that are of child bearing potential
2. Subjects without a non-culprit lesion considered appropriate to plan a staged PCI.
3. Clinically significant haematologic, hepatic, metabolic, renal, rheumatologic, anaphylactic reactions, neurological or psychiatric disease
4. Clinical evidence of any other disease, which might interfere with the subject's ability to enter the trial.
5. Concomitant administration of medications that may interfere with treatment as assessed by the Investigator, including allergy to any component of the therapy.
6. Concomitant administration of any medication prohibited for use during this study (e.g. colchicine)
7. Male subjects consuming greater than 60g alcohol per day, or female subjects consuming greater than 40g alcohol per day.
8. Evidence of any recent history of, or current recreational drug abuse
9. Serious adverse reaction or hypersensitivity to therapeutic drugs.
10. Unable and to comply with the study requirements.
11. Subjects who have been involved in an experimental drug protocol within the past four weeks.

A list of subjects screened but deemed ineligible will be maintained indicating reason(s) for exclusion.

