4.5 Randomisation and Randomisation Schedule

For the purposes of this study, participants will be randomised at screening visit.

Subjects recruited into the study who are then deemed eligible for Randomisation at Screening Visit will be randomised in a double-blinded 1:1 manner, either to active study medication or matching placebo.

Randomisation will be performed centrally by CDD. Sites will need to contact CDD to randomise study participants. CDD will be responsible for allocation of study medication based on the randomisation number. Randomisation numbers will be given out to site over the phone and confirmed electronically via signed, emailed randomisation confirmation sheet.

CDD is not a clinical site for the conduct of the trial so study investigators involved in any study participant recruitment, assessment and eventual follow-up will remain blinded to the medication therapy assignment.

Investigators/Sub-Investigators will be instructed to contact CDD on the number below;

CDD
Research Department
[name] then dial '2' for the Research Department

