11. STATISTICAL PROCEDURES

11.1 *Analysis Variables*

Analysis of efficacy will be performed according to intention-to-treat method and include all subjects who received the combination antibiotic therapy. However as the primary efficacy analysis is of subjects with paired FFR assessments, only such subjects will be included in the primary analysis. All other subjects will be included in secondary analyses. Numerical data will be presented as mean \pm SD for normally distributed variables and as median with interquartile range for non-normally distributed data. Non-normally distributed data will be log-transformed (e.g. CRP levels) before being used for comparisons. Significant changes in subjects' arterial flow, clinical symptoms and biochemical variables over time compared with that baseline will be assessed using an analysis of covariance. Differences between treatment and control groups in the occurrence of FFR \geq 80 will be assessed using Fisher's exact test. All tests will be 2-tailed with a 5% significance level.

11.2 *Interim Analysis*

A DSMB directed interim analysis is planned when 60 paired FFR data are available. At this time point, the trial would declare the combination therapy as effective if the p value is less than 0.05. However, the trial might still continue to collect extra data to accurately characterise side effects as advised by the DSMB.

11.3 *Sample Size Justification*

This is a feasibility study designed to provide preliminary observations and generate hypothesis for future studies. The sample size of 60 subjects with paired FFR was not defined on the basis of a clinical endpoint hypothesis but rather to provide information about antibiotic combination therapy efficacy and safety. The sample size required is established by assessment of the minimum number of subjects needed to provide reliable and non-trivial results. The sample size is in the range of the intervention group in the azithromycin clinical trial of subjects with CAD (n=60).

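### The plan raises a possible acute effect of ACS on non-culprit FFR, but states no stratification by ACS and compares FFR response with an unadjusted Fisher's test in about 60 subjects

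*Combined protocol and SAP*

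**What the plan says.** - **Section 1.1 (Current Treatment)** says that non-culprit FFR in ACS subjects may be acutely worse because of endothelial dysfunction, and that "randomisation should minimise confounding". It gives no size for the effect and names no other safeguard.
- **Section 4.1, criterion 3** admits "Subjects with documented recent acute coronary syndrome (ACS) or evidence of myocardial ischemia". Either route qualifies. The expected ACS share is not given and the period that counts as recent is not defined.
- **Section 3** defines success through subjects who start with FFR below 0.80 and reach 0.80 or more at 3 months. The target is a 20% difference, also expressed as 6 or more subjects.
- **Section 4.5** says "Randomisation will be performed centrally by CDD" and that subjects "will be randomised in a double-blinded 1:1 manner, either to active study medication or matching placebo". It mentions no stratum, block or minimisation.
- **Section 11.1** compares the occurrence of FFR at or above the threshold by Fisher's exact test, two-sided at 5%, and limits the primary analysis to subjects with paired FFR. It names an analysis of covariance for change from baseline but lists no covariates. ACS status does not appear in the analysis.
- **Section 11.3** refers to "The sample size of 60 subjects with paired FFR" and describes a feasibility study. **Section 3** says that, "assuming a dropout rate of 25%, approximately 80 subjects will be approached".

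**The concern.** If a recent ACS temporarily depresses the baseline FFR, some of these subjects could cross back over 0.80 by 3 months without any drug effect. The endpoint would count that as a response. A concurrent placebo group deals with this on average, but with about 30 subjects per arm the one allocation that occurs may put clearly more ACS subjects in one arm. An unadjusted test would then read part of the difference in case mix as a difference between treatments, in either direction. Section 11.2 would declare the combination effective at p below 0.05 once 60 paired results are available, so the reading of a single unbalanced trial matters. An adjustment chosen after the data had been seen would carry little weight.

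**Working it through.** **The plan's own figures.** 60 / (1 − 0.25) = 80, as Section 3 states. With 30 per arm, 0.20 × 30 = 6, also as stated. No power is given, so there is none to reproduce.

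**Assumptions not in the documents.** ACS share 30%, 50% or 70%. Spontaneous crossing to 0.80 or above in 10% of non-ACS and 30%, 40% or 50% of ACS subjects, a gap of 20–40 points. Steps 3 and 4 use a 50% ACS share. Thirty analysed subjects per arm follows from 1:1 allocation.

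**Step 1: chance imbalance.** With the ACS total fixed, the SD of the between-arm difference in ACS share is √(4p(1 − p)/59), which is 0.119 at p = 0.3 or 0.7 and 0.130 at p = 0.5.

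| Difference in ACS subjects, either direction | ACS total fixed (hypergeometric) | Independent binomials |
|---|---|---|
| 3 or more (10 points) | 40–44% | 48–52% |
| 6 or more (20 points) | 16–20% | 12–16% |

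**Step 2: shift in the arm difference.** Shift = (imbalance / 30) × recovery gap. For 18 v 12 this is (6/30) × 20, 30 or 40 = 4, 6 or 8 points. That is 1.2 to 2.4 subjects out of 30, or 20–40% of the 20-point target.

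**Step 3: effect with no drug effect (exact enumeration, 30 per arm).**

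| ACS split, ACAC v placebo | Chance of 6 or more extra ACAC responders | Chance of significant Fisher result favouring ACAC |
|---|---|---|
| 15 v 15 | 3–4% | 0.7–0.9% |
| 18 v 12 | 8–17% | 2.5–4.2% |

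Averaged over all allocations, the two-sided type I error of Fisher's test is 2.2–2.6%.

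**Step 4: what an ACS-stratified exact test changes.** The test conditions on the response totals within each ACS stratum. Simulation with 30 ACS and 30 non-ACS subjects, 40,000 runs per setting, power for a 20-point effect:

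| ACS / non-ACS crossing | Simple allocation: Fisher → stratified exact | Stratified allocation: Fisher → stratified exact |
|---|---|---|
| 30% / 10% | 29.7% → 34.1% | 29.1% → 31.0% |
| 40% / 10% | 27.4% → 33.7% | 25.8% → 30.1% |
| 50% / 10% | 25.3% → 33.8% | 23.1% → 30.6% |

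The gain from changing the test is roughly 2–8 points. The stratified exact test holds type I error at about 3% or below. Stratifying the list while keeping Fisher's test lowers power slightly, so the analysis has to follow the allocation.

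**The case against.** The strongest case on the other side is that the design already handles this. The comparison is with a concurrent, blinded, randomised placebo group, so spontaneous recovery is counted in both arms and ACS is balanced in expectation. This stands.

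Three stronger readings are tempting, and the documents do not support them:

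- **That ACS is a known prognostic factor that lowers FFR.** Section 1.1 says only that FFR may worsen. It gives no size and says nothing about recovery by 3 months, which is an inference.
- **That allocation is unstratified.** Section 4.5 is silent on how the list is built. The supportable statement is that no stratification is stated.
- **That the comparison is uncontrolled or biased.** Average type I error is 2.2–2.6%, below 5%.

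The size can also be challenged. An imbalance of 6 or more specifically towards ACAC has a chance of 6–8% (binomial) or 8–10% (half of 16–20%). The typical imbalance is 2–3 subjects, a shift of about 1.3–4 points (2/30 × 20 to 3/30 × 40). A shift of 4–8 points is below one standard error of the arm difference: √(2 × 0.2 × 0.8/30) = 10 points at 20% response and 12 points at 30%. Fisher significance needs a gap of about 8–9 subjects (5 v 13 gives p = 0.047). The mechanism in Section 1.1 concerns non-culprit vessels in multivessel disease, whereas criterion 4 also admits subjects with a single lesion, so fewer subjects may be exposed than the ACS share suggests. All of this stands and limits the size of the point.

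It does not remove the point. Long-run validity does not help the reader of one unbalanced trial. Because only subjects with paired FFR are analysed and 25% dropout is assumed, balance at randomisation need not carry over to the analysed set.

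**Conclusion.** The point holds as a matter of precision and of protection against chance imbalance, and should be acted on. It is not an error that invalidates the test. The plan raises the factor itself, records it through an entry criterion, and then uses it neither in the stated allocation nor in the analysis. An imbalance of 6 or more has a 12–20% chance in both directions together, and would shift the arm difference by 4–8 points against a target of 20. These figures rest on an assumed ACS share of 30–70% and an assumed recovery gap of 20–40 points. If ACS subjects do not recover more often than others, the shift is zero. The benefit of the change is mainly a result that can be read in the single trial, with a modest gain in power.

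**What to change.** 1. In Section 4.1 or 4.5, define ACS and non-ACS presentation at entry so that the two categories are mutually exclusive. The two routes in criterion 3 can overlap, so a written rule is needed.
2. In Section 4.5, state how the list is generated. If allocation has not started, stratify it by this one binary factor, with permuted blocks of varying size in each stratum.
3. In Section 11.1, whether or not allocation has started, and before unblinding, pre-specify an exact test stratified by ACS status for the FFR response in place of the unadjusted Fisher's test. Name baseline FFR and ACS status as covariates in the FFR analysis of covariance.

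The cost is a definition of ACS status, a second list at the central unit and a few sentences of analysis text. Presentation already has to be established for eligibility, so no new assessment is needed. If allocation is under way, only steps 1 and 3 apply, together with a description of the list actually in use. ACS status should then be classified from entry data by staff who do not know the allocation.

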1.2 RATIONALE

Chlamydomphila pneumoniae has been evaluated as one potential underlying cause of CHD. The strongest evidence supporting this hypothesis comes from multiple investigators who enrolled over 19,217 subjects in 'Anti-Chlamydia trials'¹⁷. However, these studies can be questioned on the basis of the type and duration of therapy. The recent change of the genus no longer permits treatment of *C. pneumoniae* as if it were *Chlamydia trachomatis* - which can generally be cured with a short course of macrolides [azithromycin, roxithromycin or clarithromycin] used in the majority of subjects analysed in this meta-analysis²³. *C. pneumoniae* is largely intra-cellular and its preferred locations (arterial muscle cells and macrophages) may contribute to its persistence in the body¹⁷. *C. pneumoniae* can be refractory to antibiotic treatment²⁴ in spite of in vitro susceptibility to various macrolides and ansamycins likely due to the use of sub-optimal dosages, which has been shown to encourage or induce persistence of *C. pneumoniae in vitro*²⁵. Rupp et al (2009) reported *C. pneumoniae* to infiltrated apoptotic neutrophils that are subsequently taken up by monocyte-derived macrophages, thereby preventing clearance by the body's immune system and preventing susceptibility in the presence of antibiotics²⁶.

The previously reported trials have used short-term or recurrent treatment²³. The rationale for combined antibiotic long-term therapy stems from experience with other intracellular bacteria e.g. *Mycobacterium tuberculosis*, characterized by its dormant forms and affinity for developing resistance. The presence of infection in arterial cells with associated fibrosis and calcification for a considerable time may warrant prolonged treatment to enable antibiotic penetration into infected spaces. The occurrence of dormant forms also requires long-term treatment to anticipate the 'awakening' of dormant bacterial cells so that antibiotics can be effective during their division phase. The use of a combination therapy rather than a single agent to address dormant forms is concurrent with experience with other chronic and multiple resistant strain infections such as *H. pylori*, *M. tuberculosis*, and *Mycobacterium avium paratuberculosis* which are treated with combination antibiotics to minimise the development of resistant strains. Indeed, in the *C. pneumoniae*/CHD trials, the only trial that showed marked improvement in primary end points was the trial that used multiple antibiotics albeit for 7 days²². Hence, it would be reasonable to trial an appropriate multiple-antibiotic regimen in CHD

In this trial, antibiotics against *C. pneumoniae* known to be active within cells will be used. The three drugs will be administered simultaneously to minimise resistance development, and these will be used for a minimum of 3 months. At this stage ideal duration of treatment is not known.

In preliminary clinical experience of 5 subjects, with 3-6 month treatment using clarithromycin, rifabutin and doxycycline, subjects noted reduced shortness of breath, angina episodes, and marked improvement in claudication. The dosage schedule for this trial will be initiated as half doses in the first week followed by full dosages from week two onwards. This is designed as to minimize the onset of potential adverse effects in subjects. The dose-escalating schedule allows introduction of the medications into the body and maximizing bioavailability yet minimizing the potential adverse events.

The experience with long term use of a combination of three antibiotics in *Mycobacterium avium paratuberculosis* and Crohn's disease has been largely in younger subjects who did not receive anti-platelet agents as concomitant therapies, and thus, macrolide anti-platelet agent interactions have not been observed. In the proposed group of subjects with CHD disease, clarithromycin has a known interaction with anti-platelet agents and therefore in this group, clarithromycin will be substituted by azithromycin, a similar macrolide that demonstrates the same intracellular activity against *C.*

pneumoniae but does not exhibit such interaction with anti-platelet agents. The azithromycin dose will be reduced due to its longer half-life, resulting in longer bioavailability duration in the body. Due to reported occasional QT-prolongation at high doses of azithromycin, ECG monitoring of the QT-interval will be carried out.

2. STUDY OBJECTIVES

2.1 Primary Objectives

1. To evaluate the effect of antibiotic combination therapy on objective measures of improvement in coronary flow as determined by fractional flow reserve (FFR) in subjects undergoing PCI with non-critical lesions in non-culprit arteries.

2.2 Secondary Objectives

1. To evaluate the effect of an antibiotic combination therapy on plaque morphology and volume as assessed with intra-coronary imaging (IVUS and OCT) in a substudy.
2. To evaluate angiographic stenoses changes (QCA) during the ACAC trial.
3. To examine safety and major adverse clinical events (MACE) during the ACAC therapy.
4. To record major adverse clinical events (MACE). Including death, recurrent myocardial infarction, stroke and major bleeding.

2.3 Exploratory Objectives

1. To evaluate the use of LAMP for the detection of *C. pneumoniae* in blood samples.
2. To evaluate the changes in indices of pressure and flow (as measured with the pressure/flow FFR wire) in the culprit and non-culprit coronary arteries

3. STUDY DESIGN

This is a Phase II a, prospective study comprising of 60 subjects referred to Liverpool Hospital and Sydney Southwest Private Hospital who have paired FFR assessments. To achieve this number, assuming a dropout rate of 25%, approximately 80 subjects will be approached. These subjects will be undergoing investigation for **symptomatic CHD**. Once consent has been obtained and the subject has met all the inclusion criteria without exclusions, they will be included in the study. The study is a randomised, placebo controlled trial at a randomisation rate of 1:1.

The primary endpoint will be a 20% reduction in the rate of FFR <0.80 in subjects planned to undergo staged PCI at 3 months among those randomly assigned to ACAC therapy. That is a difference of 6 or more in the ACAC group who had an FFR <0.80 at onset will have a FFR ≥0.80 at 3 months than in control group.

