4.3 Recruitment

Two centre's will participate, enrolling subjects until 60 have completed study participation defined as completing paired FFR assessments per protocol. Subjects meeting the diagnostic criteria for myocardial ischemia or a recent acute coronary syndrome whose cardiologist recommends angiography will be eligible.

Subjects presenting to the study centre/s will be invited to participate. All eligible subjects who are willing to participate will be given the opportunity to ask questions, and will be informed about the study before signing consent. Subject characteristics will be registered on a case report form that contains basic demographics and clinical characteristics age, sex, medical history, smoking and drinking habits, concomitant medications and current symptoms. In addition, a physical examination will be performed by the Investigator or sub-investigators including height, weight and vital signs.

Subjects who fail the inclusion/exclusion criteria will be informed that they are not eligible for inclusion into the study and will be treated by the Investigator as per standard clinical practice.

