4.4 Number of Subjects

A total of 60 subjects will complete study participation. Withdrawn and delayed exclusions may be replaced, see Section 9.2.

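### Section 3 sets six extra responders as the primary endpoint, Section 11 declares efficacy at p<0.05, and the plan does not say which decides; 6 to 8 extra can meet the first and miss the second

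*Combined protocol and SAP*

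**What the plan says.** Section 3 (Study Design) defines the primary endpoint as a reduction already achieved: 20% in the rate of FFR below 0.80 at 3 months among subjects assigned to ACAC. It converts this to a count: "That is a difference of 6 or more in the ACAC group who had an FFR <0.80 at onset" and at or above 0.80 at 3 months, relative to control.

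Section 11.1 takes "Differences between treatment and control groups in the occurrence of FFR" at or above the cut-off (printed there as 80) and assigns Fisher's exact test to them. It adds: "All tests will be 2-tailed with a 5% significance level". Section 11.2, on the analysis at 60 paired FFR assessments, says "the trial would declare the combination therapy as effective if the p value is less than 0.05".

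On numbers, Section 3 says "The study is a randomised, placebo controlled trial at a randomisation rate of 1:1", and Section 4.3 describes "enrolling subjects until 60 have completed study participation defined as completing paired FFR assessments per protocol". Section 4.4 repeats the total of 60. No section fixes the number of completers per arm.

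Section 11 does not mention six subjects, and Section 3 does not mention a test.

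**The concern.** As worded, Section 3 is satisfied by a count and Section 11.2 by a p value. The plan does not say whether six is a success criterion, a target effect or a condition to be met together with p<0.05. If the two can disagree on the same data, the trial could be reported as meeting its primary endpoint when the planned test does not support efficacy, and the choice of reading could be made after the results are known. The answer also has a practical consequence: Section 12.11 makes continued access to the study drug depend on the therapy being deemed beneficial.

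**Working it through.** **Inputs.** 60 subjects with paired FFR (Sections 4.3, 4.4, 11.1); 1:1 randomisation (Section 3); Fisher's exact test, two-sided, 5% (Section 11.1); threshold of six (Section 3). An even split of 30 per arm is an inference. The control response rate is not in the documents, so a range is assumed.

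**The plan's own figure.** 0.20 × 30 = 6. The stated six is reproduced if 20% means 20 percentage points of 30 subjects.

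**Test.** With a of n_A ACAC responders, c of n_C control responders and k = a + c, the probability of x ACAC responders is P(x) = C(n_A, x)·C(n_C, k − x) / C(n_A + n_C, k). The two-sided p is the sum of P(x) over all x with P(x) ≤ P(a). For 6 v 0: P(6) = C(30,6)/C(60,6) = 593,775/50,063,860 = 0.0119. The mirror table is equally likely, so p = 0.024.

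**Exactly six extra, 30 v 30 (ACAC v control).**

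| Table | p |
|---|---|
| 6 v 0 | 0.024 |
| 7 v 1 | 0.052 |
| 8 v 2 | 0.080 |
| 9 v 3 | 0.104 |
| 12 v 6 | 0.158 |
| 30 v 24 | 0.024 |

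Only the first and last rows pass among all 25 such tables.

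**All differences, 30 v 30.**

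| Extra ACAC responders | Possible tables | Tables with p≥0.05 | Control counts that miss |
|---|---|---|---|
| 5 or fewer | – | all | all (smallest p 0.052) |
| 6 | 25 | 23 | 1–23 |
| 7 | 24 | 18 | 3–20 |
| 8 | 23 | 11 | 6–16 |
| 9 or more | – | 0 | none (largest p 0.038) |

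For differences of 6 to 8 together, 23 + 18 + 11 = 52 of 25 + 24 + 23 = 72 tables miss. This counts tables and is not a probability. Fisher needs a difference of 7 with 1–2 control responders, 8 with 3–5 and 9 with 6–16. At this split every favourable significant table also has at least six extra, so disagreement runs one way.

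**Probability of disagreement, true gain of 20 points, 30 v 30.** Independent binomial counts, summed over all tables:

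| Control rate | P(six or more extra) | P(six or more, p≥0.05) | Ratio |
|---|---|---|---|
| 0% | 0.573 | 0 | 0 |
| 5% | 0.570 | 0.133 | 0.23 |
| 10% | 0.565 | 0.194 | 0.34 |
| 20% | 0.560 | 0.262 | 0.47 |
| 30% | 0.557 | 0.297 | 0.53 |

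**No true effect, 30 v 30.**

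| Common rate | P(six or more extra) | P(Fisher p<0.05 favouring ACAC) |
|---|---|---|
| 10% | 0.009 | 0.005 |
| 20% | 0.037 | 0.011 |
| 30% | 0.060 | 0.013 |
| 50% | 0.078 | 0.014 |

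**Other splits of 60.** At 29 ACAC/31 control, 7 v 1 (p=0.024) and 8 v 2 (p=0.039) pass, 9 v 3 (p=0.054) and 12 v 6 (p=0.091) still miss, and a difference of 8 always passes. The reverse disagreement also appears: 5 v 0 gives p=0.022 without reaching six. At 31/29, 7 v 1 misses (p=0.054) and a difference of 9 misses at control counts 11–16. For a true 20-point gain at control rates of 5, 10, 20 and 30%, the chance of meeting six but missing Fisher is 2%, 8%, 16% and 19% at 29/31, and 13%, 20%, 29% and 32% at 31/29.

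**The case against.** The best defence is that the plan has only one explicit decision rule. Section 11.2 alone speaks of declaring efficacy, Section 11.1 attaches Fisher's test to the same dichotomy, and the sentence in Section 3 merely translates 20% into subjects. On that reading six is a clumsily worded target effect and Section 11 governs. This may well be what was intended, but it has to be inferred. Section 11.2 is headed as an interim analysis, does not name its test and does not refer to the Section 3 endpoint. Section 11.3 says the sample size was not derived from a clinical endpoint hypothesis, so six is not presented there as a planning effect either. Section 3 calls it the endpoint.

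Four further points stand in part.

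- The 13% to 30% figures assume a real benefit and largely reflect low power. For the risk of a false claim, the no-effect comparison is the relevant one, and its figures are smaller.
- The range of 6 to 8 is exact only at 30 v 30 and moves with the split.
- Requiring both criteria would also remove the ambiguity.
- This is described as a feasibility study, which limits the consequences, but it still carries a 5% test and a rule for declaring efficacy.

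**Conclusion.** The concern holds. The count in Section 3 and the p value in Section 11 are unreconciled criteria for the same outcome, and they can give different answers: at 30 v 30 the endpoint as worded can be met at p=0.158. The count is the looser criterion at that split. With no effect and a common response rate of 20% to 50%, it is met in 3.7% to 7.8% of trials, against 1.1% to 1.4% for a favourable Fisher result. With a true 20-point gain, the two disagree in 13% to 30% of trials at control rates of 5% to 30%, and never at a control rate of 0%. These figures rest on 30 completers per arm and on assumed response rates. The lack of a stated order between the criteria rests on neither. The point should be fixed, though the repair is short and the design need not change.

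**What to change.** In Section 3, define the primary endpoint as the proportion of subjects with FFR at or above 0.80 at 3 months. State that efficacy is concluded only if the two-sided Fisher exact test gives p<0.05 in favour of ACAC, and name that test in Section 11.2. Keep the six-subject figure only as a descriptive target, labelled as an absolute difference of 20 percentage points, which is six subjects if there are 30 per arm. A proportion also removes the raw count's failure to adjust for an uneven split.

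While editing, state the denominator. Section 3 counts subjects below 0.80 at onset whereas Section 4.1 admits those at or below 0.80, and the two must be reconciled.

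The cost is wording in Sections 3 and 11.2, plus that reconciliation. Sample size and procedures are unaffected. The sponsor gives up the option of reporting six extra responders, on its own, as meeting the primary endpoint.
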